### **9.3.      Pharmacokinetic Assessments**

Blood for PK will be drawn at the following time points:

- For Dose #1: within 15 minutes predose, and at 1 ( $\pm 15$  min), 2 ( $\pm 15$  min), 6 ( $\pm 30$  min), and 12 ( $\pm 30$  min) hours after the end of dose administration (but prior to Dose #2)
- For Dose #3: within 15 minutes predose, and at 1 ( $\pm 15$  min), 2 ( $\pm 15$  min), 6 ( $\pm 30$  min), 12 ( $\pm 30$  min) and 24 ( $\pm 30$  min) hours after the end of dose administration

Samples should be spun and plasma frozen and sent to a central lab for analysis. Plasma samples will be analyzed for maximum concentration ( $C_{max}$ ), time to maximum concentration ( $T_{max}$ ), terminal half-life ( $T_{1/2}$ ), area under the curve from time zero to 8 hours ( $AUC_{0-8}$ ), area under the curve from time 0 to infinity ( $AUC_{inf}$ ).

Participants who refuse some or all PK blood samplings can remain in the trial. However, PK sampling is to be highly encouraged.

For Dose #3, the last PK sample will occur on Day 3 (i.e., 24 hours after the end of third study drug administration which was initiated 36 hours after the first dose).

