^a Day 1 is the first day of study treatment. Baseline tests (including blood draws) should be performed prior to administration of the first dose. Screening tests may also be performed on Day 1 prior to study treatment if necessary, as long as these tests cannot affect eligibility. If Dose 1 is administered in the evening of Day 1, Dose 2 would be given on the second calendar day and Dose 3 would be given on the third calendar day.

^b Test/assessment does not have to be repeated if performed within the prior 24 hours unless dictated by SOC.

^c Collect sputum sample as soon as possible if not collected at the time of hospital admission. The microbiology lab is encouraged to also perform sputum Gram-stains, antigen detection, immunoassay, and RT-PCR diagnostic tests when available. If fevers or chills are present, 2 sets of blood cultures are recommended at the discretion of the caregivers.

^d To be performed if/when indicated by SOC.

^e At screening, document radiographic evidence (CXR, or CT scan if CXR is inadequate) of COVID-19 pneumonia if not already completed in the previous 48 hours per SOC. On Days 14 and 28, repeat RT-PCR for COVID-19 and repeat CXR, or CT scan if CXR is inadequate, are encouraged but not mandatory.

^f Record blood pressure, oral temperature, respiration rate, and heart rate, as well as pulse oximetry. To be measured during study drug administration at the following time points: predose, at the end of administration, and 30 minutes after the end of administration.

^g When EKGs are to be collected at the same time point as a blood collection, EKGs should be collected first. At screening, 3 serial, resting, supine 12-lead EKGs are to be conducted within 10 minutes total time. All other ECGs are single recordings.

^h Blood for PK will be drawn for Dose #1 within 15 minutes predose, and at 1 (± 15 min), 2 (± 15 min), 6 (± 30 min), and 12 (± 30 min) hours after the end of administration (but prior to Dose #2); and for Dose #3 within 15 minutes predose, and at 1 (± 15 min), 2 (± 15 min), 6 (± 30 min), 12 (± 30 min), and 24 (± 30 min) hours after the end of administration. Samples should be spun and plasma frozen and sent to a central lab for analysis.

ⁱ Blood for PK will be collected 24 hours after the end of study drug administration given on Day 2 so the last sample will be obtained Day 3.

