10.4 Full Analysis Set

All subjects given ≥ 1 dose of study drug will be included in the Full Analysis Set (FAS) according to actual drug received.

The FAS is the primary analysis set to analyze all efficacy endpoints. Subject disposition, demographic and baseline characteristics of the FAS will also be presented. Subjects will be analyzed according to the treatment group they actually received. Differences between planned and actual treatment, if any, will be discussed during the blinded review meeting.

Note: if a subject had inadvertently taken the study drug without randomization and/or had negative COVID RT-PCR results post study drug administration, the subject would still be included in the Full analysis set.

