10.7 PK Analysis Set

The PK Analysis Set will include all subjects in the FAS who have sufficient concentration data to obtain reliable estimates of the key PK parameters and have no important protocol deviations that can influence the validity of the data for the PK endpoints.

PK Analysis Set will be finalized after review of concentration data post DBL and unblinding.

11 Analysis Variables

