12.9.7 Immunogenicity

Number and percentage of subjects for presence of antibodies against rhu-pGSN will be summarized by treatment and visit. Percentages will be based on the FAS analysis set.

All Immunogenicity parameters will be listed for FAS analysis set.

In DDP: Table 14.6.1.1 and Listing 16.2.10.4

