16.1 Summary of Statistical Analyses

Endpoints	Analysis Set	Primary Analyses	Supportive Analyses
Incidence of SAEs in rhu-pGSN vs placebo groups	Safety analysis set	Descriptive Summaries	-
Proportion of subjects alive not on vasopressors, mechanical ventilator, and dialysis on Day 14.	FAS (primary), Per-Protocol analysis set	Cochran-Mantel-Haenszel (CMH) method	-
Adverse Events, Clinically Significant Laboratory Results	Safety analysis set	Descriptive Summaries	-
Change in WHO Severity Score	FAS, Per-Protocol analysis set	Shift summaries, Box Plots, MMRM	-
Mortality Rate and Time to Death	FAS (primary), Per-Protocol analysis set	Log Rank Test, Cox Regression Model, Kaplan-Meier Curve	-
Proportion of Subjects alive without support	FAS (primary), Per-Protocol analysis set	CMH	-
Days on the Ventilator	FAS (primary), Per-Protocol analysis set	Descriptive Summaries, Wilcoxon Rank Sum Test	-
Hospitalization and ICU days	FAS (primary), Per-Protocol analysis set	Descriptive Summaries	-
Plasma Concentration	PK analysis set	Descriptive Summaries and Plots	
PK Parameters	PK analysis set	Descriptive Summaries	-
Immunogenicity	PK analysis set	Descriptive Summaries	-
Biomarkers	Safety analysis set	Descriptive Summaries	-

17 Change Log

Version	Authored by	Change Date	Change Details	Reviewed by	Review Date
1.00	[name] [name]	05-Aug-2021	First version approved	[name]	05-Aug-2021

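### SAP 12.9.7 puts antibody percentages on the whole FAS and SAP 16.1 puts them on the PK set; neither is the group with an antibody result at the visit

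*SAP*

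**What the plan says.** - SAP 12.9.7 (Immunogenicity): "Number and percentage of subjects for presence of antibodies against rhu-pGSN will be summarized by treatment and visit". The denominator follows: "Percentages will be based on the FAS analysis set". The listing is also for the FAS.
- SAP 16.1 (Summary of Statistical Analyses): the analysis set in the Immunogenicity row is the "PK analysis set".
- SAP 10.4 defines the FAS: "All subjects given ≥ 1 dose of study drug will be included in the Full Analysis Set (FAS) according to actual drug received". Being alive or having an antibody sample at a later visit is not required. SAP 10.5 notes that the Safety set is the same set.
- SAP 10.7 defines the PK set as "all subjects in the FAS who have sufficient concentration data to obtain reliable estimates of the key PK parameters", with no important deviation affecting the PK endpoints. Its membership is settled after database lock and unblinding.
- Antibody samples are due predose on Day 1 and on Days 28 and 90 (SAP 7.2.4). Dose-related PK sampling ends much earlier: footnote i of the SAP assessment schedule says "so the last sample will be obtained Day 3". It can also be declined. Protocol 9.3: "Participants who refuse some or all PK blood samplings can remain in the trial".
- Protocol 11.1 has immunogenicity assessed in all participants. The objective (Protocol 5.1.3, SAP 3.3) is antibody development after treatment, rhu-pGSN versus placebo, relative to baseline.

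**The concern.** The same table is assigned to two different populations, and neither is the set of subjects who have an antibody result at the visit in question. Deaths and losses before Days 28 and 90 are to be expected in severe COVID-19 pneumonia; mortality at those same two days is an endpoint (SAP 7.2.1, 7.2.2). A subject with no sample stays in an FAS denominator and cannot enter the numerator. If sampling loss differs between arms, equal rates among sampled subjects will look unequal.

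For a safety-type measure, an understated antibody percentage errs in the non-conservative direction. Protocol 4.7.1 describes a safety database of 24 recipients, some with apparent anti-drug antibodies, though without recognised ill effects. Protocol 4.4.2 reports no antibody formation in the inhaled study in healthy volunteers.

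A by-visit count of presence also mixes antibody already there on Day 1 with antibody that appears after dosing. The objective concerns the latter.

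**Working it through.** The documents state no antibody rate, sampling fraction or power for immunogenicity, so there is no figure of the plan's own to reproduce. The check compares the texts and then works the arithmetic on assumed values.

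**1. The two populations.** The FAS is everyone dosed at least once. The PK set is a subset selected on concentration data. A subject who declines PK sampling but gives blood on Days 28 and 90 is in the FAS, has an antibody result, and may be outside the PK set. A subject with a full PK profile to about Day 3 who dies on Day 20 is in both sets and has no Day 28 result. The sets differ from each other and from the sampled subjects.

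**2. The SAP's convention elsewhere.** SAP 12.10.3.2 bases laboratory category percentages on non-missing results at each visit. SAP 12.4 also uses non-missing results. SAP 11.3.3 creates missing/not-done records only for the WHO and CURB-65 scores, so it does not cover antibodies.

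**3. FAS denominator.** Let r be the positive rate among sampled subjects and u the share of the FAS unsampled at the visit. Then

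reported percentage = r × (1 − u).

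With r = 20% (assumed):

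| Unsampled u | Reported |
|---|---|
| 0% | 0.20 × 1.00 = 20% |
| 5% | 0.20 × 0.95 = 19% |
| 10% | 0.20 × 0.90 = 18% |
| 20% | 0.20 × 0.80 = 16% |
| 30% | 0.20 × 0.70 = 14% |

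The relative shortfall is u whatever r is: at u = 20%, 10% reads 8% and 30% reads 24%.

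**4. Unequal loss.** With r = 20% in both arms and u = 5% in one and 20% in the other (assumed), the table shows 19% and 16%. At the planned 30 per arm in Part 1 (Protocol 7.1) that is 5.7 against 4.8 subjects, a gap of 0.9 of a subject.

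**5. In counts.** Six positives among 30 FAS subjects give 6/30 = 20.0% however many were sampled. On sampled subjects the result is 6/27 = 22.2%, 6/24 = 25.0% or 6/21 = 28.6%.

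**6. PK set.** Assume 30 FAS subjects, 24 of them in the PK set; 26 sampled on Day 28, 21 of them in the PK set; and 5 positives in all. Sampled-subject rate: 5/26 = 19.2%. FAS rate: 5/30 = 16.7%. PK-set rate with 3, 4 or 5 of the positives inside the set: 3/24 = 12.5%, 4/24 = 16.7%, 5/24 = 20.8%. The error has no fixed direction.

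**The case against.** The strongest reply is that this is a clerical slip in a descriptive table. SAP 12.9.7 names the FAS twice, the protocol agrees with it, and only an appendix row differs. No test or decision rests on immunogenicity. Counts accompany percentages, and all results are listed by subject, so a reader could recompute on any denominator and compare with Day 1. That stands as a limit on consequence. It does not remove the conflict or supply a suitable denominator, and leaving the key contrast to be rebuilt from listings does not amount to planning it.

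Four stronger readings are tempting and not supported:

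- *That the SAP counts unsampled subjects as negative.* It does not say so. The layout is left to the Data Display Plan, which was not among the documents and may carry a missing row. SAP 12.10.4.2 and 12.10.4.3 pair a full-set denominator with a not-done category. A missing row would make the loss visible, but the stated percentage would still be r × (1 − u).
- *That both sets necessarily misstate the rate.* The FAS figure is exact where everyone is sampled, plausibly on Day 1, and the PK-set error can be in either direction.
- *That the PK set loses placebo subjects.* SAP 10.7 does not exclude them, PK draws are not limited to the active arm, pGSN is endogenous (Protocol 4.3), and SAP 12.9.5 and 12.9.6 present PK results by treatment group.
- *That the sampled-subject rate is the true rate.* It is conditional on survival and attendance, which can also differ by arm. It is the more interpretable figure, but it is not free of bias.

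**Conclusion.** The point holds in limited form. Without any assumption, SAP 12.9.7 and 16.1 assign immunogenicity to different populations, and the 16.1 choice is at odds with the protocol's all-participant assessment. Also from the text alone, the FAS percentage understates the rate among sampled subjects by exactly the fraction unsampled, and so is unaffected only at visits with complete sampling. Complete sampling is unlikely on Days 28 and 90 in this population, but how incomplete it will be is unknown. The illustrative sizes (20% read as 16% with 20% unsampled; 19% against 16% with unequal loss) rest wholly on assumed inputs and show the mechanism, not an expected result. Separately, presence by visit alone does not answer an objective framed as development relative to baseline. The primary efficacy and SAE analyses are unaffected.

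**What to change.** 1. In SAP 16.1, change the Immunogenicity row to the FAS, in line with 12.9.7 and the protocol. Naming the Safety set instead would change nothing, since the two are identical by definition.
2. In SAP 12.9.7, make the denominator at each visit the FAS subjects with an evaluable antibody result at that visit, following SAP 12.10.3.2. Show by arm and visit the number evaluable, the number dead and the number alive but unsampled. State that the rate is conditional on being sampled.
3. Add treatment-emergent antibody by arm: negative on Day 1 and positive on Day 28 or Day 90, with the number evaluable for that comparison shown.

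No new data or samples are needed. The cost is SAP wording, a small revision of the table shell in the Data Display Plan, and the matching programming.

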12.10 Safety Analyses

12.10.1 rse Events

All Adverse events will be coded using the Medical Dictionary for Regulatory Activities (MedDRA) version 23.0 or Higher. All summaries will be based on Safety analysis set.

12.10.1.1 Overall Adverse Events

Number and percentage of subjects and number of events will be summarized by treatment for the following categories:

1. All adverse events reported
2. Treatment emergent adverse events (TEAEs)
3. Serious TEAEs
4. Related TEAEs
5. Related Serious TEAEs
6. Adverse events led to death
7. Adverse events led to study discontinuation
8. Grade 3 or higher TEAEs
9. Grade 3 or higher related AEs
10. Adverse events by severity
11. Injection related Adverse Events by Severity
12. Adverse events by relationship to IMP
13. Adverse events by relationship to study procedure
14. Adverse events by outcome
15. Adverse events by action taken with treatment

Severity grading is based on NCI CTCAE, version 5.0. Percentages will be based on Safety analysis set. If a subject has multiple occurrences with different intensity/ relationships, then all the occurrences will be counted.

In DDP: Table 14.3.1.1

All adverse events will be listed by subject and system organ class. Adverse events will be grouped by subjects. Day the Adverse event started, and Duration of AEs will also be included in the listing.

In DDP: Listing 16.2.7.1

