7.2 Secondary Endpoints

7.2.1 Safety and tolerability

- *Incidence, causality, and severity of AEs (graded according to the National Cancer Institute [NCI] Common Terminology Criteria for Adverse Events [CTCAE] version 5.0) in rhu-pGSN vs placebo groups*
- *Frequencies of new or worsening clinically significant laboratory abnormalities in rhu-pGSN vs placebo groups*
- *Mortality rate irrespective of cause at Days 28 and 90*

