12.10.1.3 Summary of Adverse Events by Relationship and Intensity

Number and percentage of subjects and number of events in each system organ class, preferred term and intensity (Grade 1-5) will be summarized by relationship for treatment-emergent adverse events and treatment. System organ class and preferred term will be displayed by descending order of frequency in “Total”. Intensity will be displayed in the alphabetical order.

In DDP: Table 14.3.1.9

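### SAP 12.10.1.1 can count one subject in several severity or relationship rows, so the subject percentages overlap and no summary by worst grade is planned

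*SAP*

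**What the plan says.** SAP 7.2.1 lists "Incidence, causality, and severity of AEs" as a secondary safety endpoint. SAP 12.10.1.1 serves it with a 15-item table, introduced by "Number and percentage of subjects and number of events will be summarized by treatment for the following categories". Four items are breakdowns: "Adverse events by severity" (item 10), injection-related events by severity (item 11), relationship to the study drug (item 12) and relationship to study procedure (item 13). On the denominator it says "Percentages will be based on Safety analysis set", and on counting it says "If a subject has multiple occurrences with different intensity/ relationships, then all the occurrences will be counted".

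The same table has rows that ask only whether a subject had any event of a kind: TEAEs (item 2), related TEAEs (item 4), "Adverse events led to death" (item 6), "Grade 3 or higher TEAEs" (item 8) and related events of Grade 3 or higher (item 9). All AEs are also listed by subject (Listing 16.2.7.1).

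SAP 12.10.1.3 plans subjects and events by system organ class (SOC), preferred term (PT), Grade 1 to 5 and relationship. It gives no rule for a subject whose events differ in grade or relationship.

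**The concern.** Counting every occurrence is right for a number of events. Applied to a number of subjects, it puts someone with Grade 1, 2 and 4 events into three severity rows, and someone with a related and an unrelated event into both relationship rows. The rows no longer divide the subjects. A low-grade row shows who ever had a mild event, including subjects whose worst event was life-threatening. It therefore depends partly on how many events each subject has.

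At stake is whether a reader of the summary tables can see, by arm, how many subjects had a worst event of each grade. That is a natural subject-level description of a stated secondary endpoint, and the SAP text plans no such summary.

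**Working it through.** **Inputs.** From the documents: the counting rule, the Safety analysis set as denominator, and the list of items (all SAP 12.10.1.1). No AE rate or expected AE percentage is given, so there is no planned figure to reproduce.

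**1. When the rows exceed 100%.** Under every-occurrence counting,

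sum of subject % over grades = (% of subjects with any AE) × (mean number of distinct grades per affected subject).

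- 50% × 1.5 = 75%
- 70% × 1.5 = 105%
- 90% × 2 = 180%

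The sum can fall on either side of 100%.

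**2. Illustration (all inputs assumed).** AEs per subject are Poisson, and events fall in Grades 1 to 5 with probabilities 40/30/17/8/5%; 200,000 subjects were simulated per scenario. For means of 0.5, 1, 1.5, 2, 3 and 5 AEs per subject, the rows sum to 47%, 87%, 123%, 153%, 205% and 277%. At a mean of 2, where 86.4% of subjects have any AE:

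| Grade | Every-occurrence row, % | Worst grade, % |
|---|---|---|
| 1 | 55.0 | 16.6 |
| 2 | 45.0 | 24.7 |
| 3 | 28.8 | 22.3 |
| 4 | 14.7 | 13.2 |
| 5 | 9.5 | 9.5 |
| Sum | 153 | 86.4 |

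Check on one cell: the Grade 1 row should be 1 − exp(−2 × 0.40) = 55.1%. The worst-grade rows sum to the percentage with any AE, so they can never exceed 100%.

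**3. What the other rows recover in this example** (taking all AEs as treatment-emergent).

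- The Grade 3 or higher row is 45.1%, equal to the share with worst Grade 3 to 5. Worst Grade 1 or 2 together is 86.4 − 45.1 = 41.3%.
- Grade 5 is always a subject's worst grade, so 9.5% is exact. Worst Grade 3 or 4 together is 45.1 − 9.5 = 35.6%.
- Grade 3 versus 4: worst Grade 4 cannot exceed its row, 14.7%. Worst Grade 3 cannot exceed 28.8%, so worst Grade 4 is at least 35.6 − 28.8 = 6.8%. The rows allow 6.8 to 14.7%.
- Grade 1 versus 2: the Grade 2 row (45.0%) could lie wholly among the 45.1% with worst Grade 3 to 5, and the Grade 1 and 2 rows each exceed 41.3%. The rows therefore allow worst Grade 2 to be anywhere from 0 to 41.3%.

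**4. Relationship to the study drug.** SAP 11.12 groups relationship into related and not related. Item 4 counts each subject with a related TEAE once, and item 2 minus item 4 gives those with only unrelated TEAEs. Finer levels are not recoverable.

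**5. Where no once-per-subject row helps.**

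- *Item 11.* Subjects receive three doses (protocol 6.5), so one subject can have injection-related events of different grades. Item 8 pools all TEAEs, and no Grade 3 or higher row exists for injection-related events, although protocol 6.4 defines and manages these reactions by grade.
- *Item 13.* No separate row counts subjects once by relationship to study procedure. If only two levels are shown, the split follows by subtraction from item 1, but the SAP does not state the levels.
- *SAP 12.10.1.3.* No subject rule is stated. SAP 12.10.1.2 repeats the SOC/PT table for related, serious and related serious events but not for Grade 3 or higher, so even that split is missing at SOC/PT level.

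**The case against.** The strongest reply is that the endpoint concerns the severity of events, and the SAP reports events by grade and by arm. Worst grade per subject is then a different quantity, and counting a subject in every applicable row is a transparent convention, stated in advance and applied equally to both arms. This stands as a reason for low priority. It does not explain why subject percentages are printed beside the event counts without a rule that makes them divide the subjects.

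The sentence speaks of occurrences, and SAP 8.1 separates number of subjects from number of events, so it may govern event counts only. In that case the subject rule is unstated rather than unsuitable, and the same clarification is needed.

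Layouts are in the Data Display Plan, which is not available here. SAP 12.10.1.2 cites seven tables numbered 14.3.1.2 to 14.3.1.8 but describes four summaries, so a worst-grade table may exist there. The statement that none is planned rests on the SAP text alone.

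Three stronger conclusions are tempting, and the documents do not support them:

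- *That the percentages will add to far more than 100%.* This needs an AE rate, which is not given; the assumed scenarios run from 47% to 277%.
- *That severity by subject cannot be recovered.* Items 2, 4, 6, 8 and 9 recover the Grade 3 split, fatal events and related versus not related, and the listing holds the rest.
- *That an arm with early deaths would look milder, and that worst-grade counting would cure this.* A fatal event still appears in Grade 5 and in items 6 and 8. Worst grade also depends on the number of events: in the simulation, worst Grade 1 falls from 18.3% of subjects at a mean of 1.5 AEs to 4.3% at a mean of 5.

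**Conclusion.** The point holds as a gap in a reporting rule. On the natural reading of SAP 12.10.1.1, the subject rows by severity and relationship overlap, and neither that section nor 12.10.1.3 plans a count of subjects by worst grade. Missing from the summaries are:

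- worst Grade 1 versus 2 and worst Grade 3 versus 4;
- worst grade for injection-related events;
- a once-per-subject split for relationship to study procedure;
- worst grade by SOC and PT.

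The size depends on events per subject, which the documents do not give; the gap of 55.0% against 16.6% for Grade 1 is an assumed illustration. The data remain in the subject listing. The summary is descriptive and secondary, so neither the primary SAE incidence nor the efficacy analysis is affected. Priority is low, and the change is worth making because it is cheap.

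**What to change.** Replace the counting sentence in SAP 12.10.1.1 with: *For subject counts and percentages, each subject is counted once at the worst grade and the strongest relationship within the category, SOC or PT shown; all occurrences are counted in the number of events.* Apply it to items 10 to 13 of 12.10.1.1 and state it again in 12.10.1.3.

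The convention fits the SAP's own practice elsewhere: the highest WHO score is used for same-day repeats (11.3.4), and the worst result is used for simultaneous baseline values (11.7).

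The cost is one SAP sentence and minor programming. The percentage of subjects with any event in a given grade is no longer shown; event counts by grade are kept.
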